5 MILESTONES

Milestone	Planned date
Registration of study protocol in the HMA-EMA catalogue of real world data studies	November 2026
Start of data collection	January 2026
End of data collection	July 2026
Interim report	April 2026
Final report on study results	September 2026

7 VERSION HISTORY

Version	Date	Description of changes
1.0	18-NOV-2025	Creation of first version of the protocol

8 LIST OF ABBREVIATIONS

Abbreviation	Definition
ARD	Acute respiratory disease
COPD	Chronic obstructive pulmonary disease
CRF	Case report form
DALY	Disability-adjusted life year
DMP	Data management plan
eCRF	Electronic case report form
ED	Emergency department
EDC	Electronic data capture
ELISA	Enzyme-linked immunosorbent assay
FISABIO	Fundación para el Fomento de la Investigación Sanitaria y Biomédica de la Comunitat Valenciana.
GDPR	General data protection regulation
GPP	Good publication practice
hMPV	human metapneumovirus
ICF	Informed consent form
ICMJE	International committee of medical journal editors
IEC	Independent ethics committee
IgG	Immunoglobulin
IRB	Institutional review board
LRTI	Lower respiratory tract infection
mAb	Monoclonal antibody
PCC	Primary care center
PI	Principal Investigator
PIV	Parainfluenza virus
QC	Quality control
RSV	Respiratory syncytial virus
RT-PCR	Real-time polymerase chain reaction
SAP	Statistical analysis plan
(s)ARI	(Severe) Acute respiratory infection
SARS-CoV-2	Severe Acute Respiratory Syndrome Coronavirus 2
URTI	Upper respiratory tract infection
VAHSNI	Valencia Hospital Surveillance Network for the Study of Influenza and Other Infectious Diseases

9 GLOSSARY

Term	Description
Co-Coordinators	means FISABIO and P95, both Partners, that are the Co-coordinators.
id.DRIVE	means the public-private partnership for conducting observational studies on infectious diseases, vaccines, related preventive measures and therapeutics for infectious diseases in Europe organized under the Consortium Agreement. For the avoidance of doubt, as of January 2024 COVIDRIVE became a part of id.DRIVE as described in further detail in the Governance Charter.
Study Contributor	or "Study Site or "Site", means an institution that collects/owns data of interest for studies and that signs a Study Contributor Agreement with P95 after being selected via a study-specific selection process.
Study Results Publication	means a scientific publication reporting on the Study including all Study objectives identified in the individual Study protocol(s).
Study Team	
means the team that carries out the conduct of the Study. For Primary Data Use Studies, the Study Team includes experts from the Co-Coordinators, Study Contributors and Study Requestors.
 
 • The Restricted Study Team (Restricted ST) is made up of experts from the Co-Coordinators and Study Contributors. • The Full Study Team (Full ST) is the Restricted ST plus the experts from the Study Requestors.

10 BACKGROUND & RATIONALE

According to the Global Burden of Disease Study (pre-COVID-19), lower respiratory tract infections (LRTIs) caused nearly 66 million hospitalizations and 2.4 million deaths globally, accounting for 4.4% of all-cause mortality [1]. In 2016, LRTIs were responsible for over 91 million disability-adjusted life years (DALYs) [1]. Also, upper respiratory tract infections (URTIs) reached more than 17 billion incident cases in 2019, accounting for about 43% cases of the global disease burden and injuries, and caused about 64 million DALYs in 2019 globally [2].

Both LRTIs and URTIs are caused by a wide range of pathogens, including respiratory viruses such as influenza, RSV, hMPV, and PIVs. While many infections result in mild illness, some progress to severe disease requiring hospitalization or even resulting in death.

A recent global analysis of RSV burden found that mortality rates in individuals aged 70 years and older exceeded those in children under five, highlighting the burden of RSV among older adults [3]. In contrast, the burden of other respiratory viruses—such as parainfluenza and adenoviruses—remains poorly understood. A cross-sectional study in the United States assessed the burden of RSV, hMPV, PIV, and influenza using medical records [4]. Pooled estimates indicated that RSV, hMPV, and PIV were associated with severe respiratory disease and prolonged hospital stays in adults. The study also noted potential under-testing and underdiagnosis, suggesting that the true burden may be underestimated.

Most incidence estimates rely on RT-PCR testing of nasopharyngeal swabs. However, several studies suggest that RSV hospitalization rates in older adults may be underestimated by at least 2.2-fold due to case under-ascertainment when using nasopharyngeal swabs alone [5-8]. Similarly, detection rates for hMPV and PIV may also be underestimated when relying solely on nasopharyngeal swabs [8].

Despite growing evidence of underdiagnosis, few studies have systematically assessed the limitations of nasopharyngeal swab-based detection for RSV, hMPV and PIV, in medically-attended adults for acute respiratory infections.

With this study, we aim to gain insights into the possible underestimation of RSV, hMPV, PIV detection rates in patients with (severe) acute respiratory infections ((s)ARI) by using nasopharyngeal swabs alone compared to the use of multiple specimens (oropharyngeal, saliva, sputum and blood samples).

This study is conducted by the id.DRIVE public-private partnership, a consortium created to facilitate the conduct of observational studies on infectious diseases, vaccines, related preventive measures, therapeutics, and diagnostics for infectious diseases. id.DRIVE evolved from the COVIDRIVE consortium launched in September 2021, to address the joint need to monitor COVID-19 vaccination programs for public health institutes and assess brand-specific COVID-19 vaccine effectiveness for vaccine companies as part of their regulatory obligations. Current id.DRIVE members are FISABIO (Fundación para el Fomento de la Investigación Sanitaria y Biomédica de la Comunitat Valenciana, Spain), P95 (Belgium), AstraZeneca (United Kingdom), Novavax (US), Pfizer (US) and Sanofi (France). Past members are THL (Finnish institute for Health and Welfare, Finland), GSK

(GlaxoSmithKline, UK), Janssen (Belgium), Valneva (Austria), CureVac (Germany), Moderna (US), and Bavarian Nordic (Denmark). This pilot project is performed at the request of Sanofi (France).

11 OBJECTIVES

11.1 Primary Objective(s)

1. To assess the detection rates (%) of RSV, hMPV and PIV in adult (s)ARI patients (≥ 18 years), when using multi-specimen collection compared to a single nasopharyngeal swab, overall and by additional specimen type.

11.2 Secondary Objective(s)

2. As primary objective, stratified by:
 - Age categories: 18-49, 50-59, 60-74, 75+
 - Sex at birth
 - Time since symptom-onset categories
 - By setting (hospital, ED ward and PCC)
 - By diagnosis (upper respiratory tract infection vs. lower respiratory tract infection and pneumonia, bronchitis, bronchiolitis, etc.)
 - By common comorbidities/ chronic conditions
3. As primary objective, stratified by:
 - Vaccination status
 - RSV detection rates by RSV vaccination status (ever vaccinated or unvaccinated)
4. To assess the detection rates (%) of SARS-CoV-2 and Influenza in adult (s)ARI patients (≥ 18 years), when using multi-specimen collection compared to a single nasopharyngeal swab (overall and by additional specimen type), overall and stratified by:
 - SARS-CoV-2 detection rates by SARS-CoV-2 vaccination status (vaccinated in the last 12 months or not vaccinated in the last 12 months)
 - Influenza detection rates by Influenza vaccination status (vaccinated in the last 12 months or not vaccinated in the last 12 months).

11.3 Exploratory Objective(s)

5. To assess the detection rates (%) of co-infections (all pathogens tested) in adult (s)ARI patients (≥ 18 years), when using multi-specimen collection compared to a single nasopharyngeal swab, overall and by additional specimen type.
 - And stratify by disease severity (setting: PCC, ED ward, hospitalization, death), if the sample size allows.
6. As primary objective, stratified by subtype or serotype (when applicable)
 - RSV detection rates by RSV subtype A and B
 - PIV detection rates by PIV serotype (1-4)
7. To assess the detection rates of Influenza, SARS-CoV-2 and other viral pathogens tested for with the RT-PCR multiplex panel in adult (s)ARI patients (≥ 18 years), when using multi-specimen collection compared to a single nasopharyngeal swab, overall and by additional specimen type.

12 METHODS

12.1 Study Design

This study is a multi-setting (inpatient, ED ward and PCC) prospective cohort study of (s)ARI cases.

The outcome of interest for the study will be laboratory-confirmed infection (with one of the viral respiratory pathogens of interest) in patients visiting PCC and ED or hospitalized because of (s)ARI.

12.2 Study Setting

This is a multicenter pilot study taking place in Spain, involving up to four PCCs and one hospital—including emergency departments—in the Valencia region.

The following centers are involved:

- Hospital [name], part of the VAHNSI hospital network (inpatient and ED ward).
- PCCs based in Valencia, Spain

12.3 Study Population

The study population consists of adults aged 18 years and older, presenting at one of the participating Study Contributors during the study period, who

- meet the inclusion criteria and does not present with any exclusion criteria

AND

- meet the (s)ARI case definition (see Section 12.3.1)

12.3.1 Case definition

For the purposes of this study, the case definition of (s)ARI will serve as the main definition for identifying cases across all healthcare settings involved—hospitals, PCC, and ED. Recognizing that the classical (s)ARI definition includes hospitalization as a criterion, which is not applicable in PCC and ED contexts, we will adopt the notation (s)ARI to reflect that not all patients have severe illness. The presence of the same symptoms will be used to trigger enrolment in the study in all settings.

A (s)ARI case is defined as a patient with a suspicion of a respiratory infection with at least one of the following symptoms:

- cough
- fever (≥ 38 C°)
- shortness of breath
- sudden onset of anosmia, ageusia, or dysgeusia

with symptom onset within the last 14 days prior to hospital admission and symptoms occurring for at least 24 hours.

12.3.2 Inclusion Criteria

Individual patients need to fulfil the following inclusion criteria:

- Adults aged 18 years and older

AND

- Meet the (s)ARI case definition

AND

- Willing to have a nasopharyngeal and oropharyngeal swab collected as well as saliva.

AND

- Willing and able to provide informed consent, obtained from the patient or from the patient's Legally Acceptable Representative(s).

Patients are also asked to provide sputum and blood samples for paired serology testing; however, this is optional and consent is provided separately on the ICF.

12.3.3 Exclusion Criteria

Individuals (patient) cannot be enrolled if:

- patient cannot be swabbed due to severe septum deviation, obstruction, or other conditions that contra-indicate swabbing,
- patient was previously enrolled in the study within 30 days of their current visit/admission,
- patient develops signs and symptoms of (s)ARI after being hospitalized.

12.3.4 Definitions

Medically attended patients (PCCs and ED):

Persons who sought medical care at an ED or PCCs but are not admitted for an overnight hospital stay or admitted to the hospital directly. This includes individuals who are evaluated, treated, or managed during a single visit and discharged the same day.

Hospitalized patients:

Persons admitted to the hospital with overnight stay. An overnight stay is defined as at least one day difference between date of hospital admission and discharge date.

12.4 Study Period

Patients will be recruited from January 2026 until end of June 2026. Recruitment targets are set per setting and month based on logistics and average number of patients at each setting during the previous years.

During January and February, a maximum of 100 (s)ARI inpatients per month will be consecutively recruited during the week (Monday to Friday). Recruitment will be

halted after 100 patients are recruited. During the other months with expected high hMPV and PIV circulation, all (s)ARI patients will be approached.

For both the ED ward and PCC setting, (s)ARI patients will be recruited consecutively during the week (Monday to Friday). Each week 12 (s)ARI patients will be recruited from each setting. During the peak season of respiratory illnesses, the targets might be reached before Friday and then recruitment will be halted for that week. In slower recruitment weeks, all patients will need to be approached to reach the target sample size of 12 (s)ARI patients.

12.5 Variables

12.5.1 Outcome(s)

12.5.1.1 Primary Outcome – Laboratory-confirmed respiratory infection

A laboratory-confirmed respiratory infection is defined as either:

- a positive RT-PCR result from the nasopharyngeal, oropharyngeal, sputum or saliva respiratory sample, and/or
- a positive serology result from paired blood samples (hospitalized patients only).

The outcome of interest for the primary objectives is a laboratory-confirmed infection with one of the viral respiratory pathogens of interest:

- RSV:
 - Subtype A
 - Subtype B
- PIV
 - Serotype 1
 - Serotype 2
 - Serotype 3
 - Serotype 4
- hMPV

The RT-PCR commercial kit will be used on the nasopharyngeal, oropharyngeal, sputum or saliva respiratory samples and will test for additional pathogens as well including Influenza A and B and SARS-CoV-2.

There will be no results for these additional pathogens on the blood samples.

12.5.2 Other Variables and Covariates

At baseline, information on covariates will be collected from patients in all settings through an electronic Case Report Form (eCRF). The complete dataset can be found in the annotated eCRF and is summarized in Table 1.

Table 1. Study covariates

Covariate	Description
Age	DD-MMM-YYYY
Sex at birth	Male, female
Setting id	Hospitalized, ED ward or PCC
id.DRIVE Study Protocol https://iddrive.eu	version 1.0
	18 November 2025 Page 25 of 44

Covariate	Description
Symptom onset-date	DD-MMM-YYYY
Date of visit or admission	DD-MMM-YYYY
Diagnosis	Upper respiratory tract infection (URTI) or lower respiratory tract infection (LRTI)
Admitting diagnosis	ICD-10 code
Chronic conditions/	
Comorbidities:	
Asthma	Binary, yes/no
Chronic lung disease	Binary, yes/no
Chronic obstructive pulmonary disease (COPD)	Binary, yes/no
Chronic cardiovascular disease	Binary, yes/no
Hypertension	Binary, yes/no
Chronic liver disease	Binary, yes/no
Chronic renal disease	Binary, yes/no
Type 1 and type 2 diabetes	Binary, yes/no
Cancer	Binary, yes/no
Obesity	Binary, yes/no
Immunodeficiency disorders	Binary, yes/no
Neurological disorder	Binary, yes/no
Immunodeficiency or organ transplant	Binary, yes/no
Long-term care facility residence	Binary, yes/no
Admission to intensive care unit	Binary, yes/no
In-hospital death	Binary, yes/no
Vaccination status:	
RSV	Vaccination history of RSV vaccinations, vaccination date
Influenza	Vaccination details of Influenza vaccination within 12 months prior to (s)ARI medical attendance, vaccination date
SARS-CoV-2	Vaccination history of COVID-19 vaccinations, vaccination date
Symptoms and signs	Nasal congestion/rhinorrhea; Sore throat/hoarseness; Sinus pain/pressure tenderness; Chest pain; New or increased cough; New or increased sputum; New or increased dyspnea (shortness of breath); New or increased wheezing (reported by study participant or investigator); New or increased crackles/rhonchi/ rales based on chest auscultation (reported by investigator); Tachypnea: respiratory rate \geq 20 respirations/min (reported by investigator); Hypoxemia: Low or decreased oxygen saturation (O ₂ saturation < 95% or \leq 90% if baseline is <95%) (reported by investigator); Need for oxygen supplementation (reported by investigator); Fever (temperature \geq 38°C by any route; self-reported by patient in the case of use of fever lowering medication); Feverishness (Feeling of having fever if temperature is not

Covariate	Description
	measured or forgotten); Fatigue; Body aches; Headache; Anorexia/decreased appetite

12.6 Data Sources

After study enrolment, data will be collected from primary (e.g., laboratory results) and secondary data sources (e.g., vaccination registries, medical files). Chronic conditions and comorbidities will be collected using the medical files. The symptoms and signs a patient is experiencing are collected from the medical files as well as from the intake conversation with the treating physician.

Exposure status, brand information and date of vaccination(s) will be ascertained by consulting vaccination registries or medical records. Where needed, treating physician or other health care professionals will be contacted to obtain additional information.

12.7 Study Procedures

Patients attending to PCC, ED and patients hospitalized will be screened to select eligible (s)ARI patients¹. These patients will be approached for written informed consent. Those willing to participate in the study will be asked to provide saliva, nasopharyngeal swabs and oropharyngeal swabs, with optional sputum samples. Blood samples are collected only from hospitalized patients, with paired serology used to confirm recent infection. Study samples will be collected by trained personnel following instructions for proper identification, hygiene procedures, and sample labelling which will be outlined in the Study Assessments and Procedures form.

No treatment is provided as part of this study; routine clinical management and standard-of-care therapies will be provided to the study participants.

The following samples are taken to identify the pathogen causing the respiratory infection:

Table 2. Sample collection by setting

Sample type	ED and PCCs setting	Hospitalized
Nasopharyngeal	Required	Required
Oropharyngeal	Required	Required

¹ In the hospital setting, during January and February a maximum of 100 patients per month will be consecutively recruited during the week (Monday to Friday). During the other months with expected high hMPV and PIV circulation, all (s)ARI patients will be approached (including weekends). For both the ED ward and PCC setting, (s)ARI patients will be recruited consecutively during the week (Monday to Friday). Each week 12 (s)ARI patients will be recruited per setting. During the peak season of respiratory illnesses, the targets will be reached before Friday after which recruitment will be halted for that week. In slower recruitment weeks, all patients will need to be approached to reach the target sample size of 12 (s)ARI patients.

Sample type	ED and PCCs setting	Hospitalized
Saliva	Required	Required
Sputum (optional)	Optional	Optional
Blood sample taken at baseline in hospital (optional)	Not collected	Optional
At convalescence: Blood sample taken 28 (+/- 3 days) days after hospital admission (if baseline sample was taken)	Not collected	If baseline is taken

Respiratory samples

A laboratory-confirmed infection is a positive multiplex RT-PCR on a respiratory sample collected between hospital admission and up to 48 hours after hospital admission, preferably as soon as possible. For ED/PCC patients, sample should be collected at time of the initial visit.

All respiratory samples (nasopharyngeal, oropharyngeal, sputum and saliva samples) will be tested using a commercial RT-PCR kit, which has undergone quality and/or validation processes. Study Contributor will be requested to submit validation logs summarizing the quality check process, results, timing and certificates of analysis for assays performed.

Blood samples

Blood samples will be collected only from hospitalized (s)ARI patients. A baseline sample is taken at admission (within 48 hours), and a convalescent sample is requested 28 days (+/- 3 days) after hospital admission. If the patients have already been discharged from the hospital for the second blood sample, a study nurse will visit them at their homes to collect the required samples and information or transport will be arranged for the study participant to come to the hospital. The serum sample must be stored and transported at -20°C. Every month a batch of blood samples will be transported to the central laboratory in Lyon, France. Whenever possible, blood taken as part of the standard of care will be salvaged for this study.

[figure not shown]
ELISA technique will be used to detect and quantify IgG antibody titers. The following antibody titers will be tested:

- RSV-A IgG antibody titers baseline
- RSV-A IgG antibody titers convalescence
- RSV-B IgG antibody titers baseline
- RSV-B IgG antibody titers convalescence
- hMPV-A IgG antibody titers baseline
- hMPV-A IgG antibody titers convalescence
- hMPV-B IgG antibody titers baseline
- hMPV-B IgG antibody titers convalescence
- PIV1 IgG antibody titers baseline

- PIV1 IgG antibody titers convalescence
- PIV2 IgG antibody titers baseline
- PIV2 IgG antibody titers convalescence
- PIV3 IgG antibody titers baseline
- PIV3 IgG antibody titers convalescence
- PIV4 IgG antibody titers baseline
- PIV4 IgG antibody titers convalescence

See Figure 1 for the schematic overview of the samples that will be taken and the test to be performed.

Figure 1. Study procedure overview

12.7.1 Sample storage

To support potential future analyses and ensure the integrity and reproducibility of study findings, aliquots of any leftover material from the biological samples collected will be stored under controlled conditions for long-term preservation. This approach enables the possibility of retesting or conducting additional analyses as new methodologies or research questions arise. All samples will be aliquoted to

minimize freeze-thaw cycles and stored at validated temperatures in accordance with Good Clinical Practice and applicable biobanking standards. Participants will be providing informed consent for the storage and potential future use of their samples, which will be maintained in secure, access-controlled facilities for the duration specified in the study protocol.

12.8 Study Management

The study will be conducted by the Study Contributor investigator(s) with input, review, and approval from the P95 Research Team, including support for material development, study contributor recruitment and training, network management, electronic data capture (EDC), and data handling.

All study activities will follow the final approved protocol. The rights, safety, and well-being of patients will take precedence over scientific or societal interests. All personnel must be appropriately qualified by education, training, and experience.

12.8.1 Training

Study Contributor Investigators and data collectors will be trained on the study protocol before the start of the study. They will receive the protocol and study training material.

12.8.2 Data Capture

The data will be collected using the electronic data capture system Viedoc. Viedoc will be set up following the annotated case report form (CRF).

12.9 Statistical Methods

A statistical analysis plan (SAP) will be developed prior to the conduct of the analysis. The SAP specifies all statistical analyses, including sensitivity analyses, to be conducted and will include table shells and mock figures.

12.9.1 Sample Size Considerations

Sample size were calculated assuming paired designs across various scenarios, assuming the addition of one extra specimen per patient and the simplifying assumption that all positives by Method A are also positive by Method B (i.e., the gain equals the proportion A-/B+). These calculations were based on pathogen incidence rates ranging from 1% to 10% and varying levels of improved detection with an additional sample. Across all settings, we expect data from over 1,000 patients with at least two specimens available (approximately 450 inpatients and 624 outpatients).

Under these assumptions, with the planned combined samples ($N \approx 1,074$), we have adequate precision to assess a doubling of detection rates — consistent with the Pfizer North America Multispecimen Study [6] — for pathogens with an incidence between 1% -7% range. For such doublings, the 95% confidence intervals on the gain are expected to be approximately ± 0.6 and ± 1.8 percentage points overall (interval with ≈ 1.2 —3.6 pp), depending on the baseline incidence.

While analyses stratified by settings will be possible, they will have wider confidence intervals due to smaller sample sizes.

The analysis of the 150 patients with available serology data will be exploratory, with limited statistical power, as we expect only a small number of PIV and/or hMPV cases in this subgroup.

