- Chronic conditions/ Comorbidities:
 - o chronic lung disease
 - o chronic cardiovascular disease
 - o hypertension
 - o chronic liver disease
 - o chronic renal disease
 - o type 1 and type 2 diabetes
 - o cancer
 - o immunodeficiency disorders
 - o obesity
 - o neurological disorders
- Immunodeficiency (e.g., on immunosuppressants)
- Long-term care facility residence
- Vaccination status (RSV, Influenza, SARS-CoV-2), including date of last vaccination
- Specimen test results, specimen type, date of sampling
- Symptoms
- Date of symptom-onset

Data sources:

After study enrolment, data will be collected from primary (e.g., laboratory results) and secondary data sources (e.g., vaccination registries, medical files).

Exposure status, brand information and date of vaccination(s) will be ascertained by consulting vaccination registries. Where needed, treating physician or other health care professionals will be contacted to obtain additional information.

Study size:

Target sample size: 1074 (s)ARI patients (450 in hospital; 624 in PCC and ED):

Data analysis:

The rate of respiratory pathogen diagnosis from nasopharyngeal swab alone will be determined by dividing the count of patients in which the respiratory pathogen of interest was detected solely by nasopharyngeal swab by the total patient count involved in this study, thereby yielding detection rates. The same calculation will be performed for the other specimens, oropharyngeal swab, saliva, blood, and sputum, as well as the detection rates when different specimen types are combined. We will determine the increase in detection rates for each specimen added, using nasopharyngeal only as a reference point. Results will also be presented for different subgroups to explain potential heterogeneity. All included patients are required to have at least a nasopharyngeal swab, oropharyngeal swab and a saliva sample. Euler diagrams will be employed to illustrate respiratory pathogen diagnosis per specimen type. The sensitivity for each specimen type and combination thereof will also be computed.

Data management:

Data collected at Study Contributors will be checked for quality and transferred to a dedicated, secured central server hosted by P95. A data management plan (DMP) will be written prior to the start of the data collection. The DMP will describe all functions, processes, responsibilities and specifications for data collection, cleaning, and validation.

Quality control:

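### In Section 12.9.1 the incidence range of 1% to 7% and the precision of ±0.6 to ±1.8 percentage points do not match: at 7% the protocol's own assumptions give about ±1.5

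*Protocol*

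**What the plan says.** Protocol Section 12.9.1 (Sample Size Considerations) describes paired calculations for one added specimen. It assumes that every patient positive by the reference method is also positive by the extended method, so the gain is the proportion newly positive. The scenarios run are described as "pathogen incidence rates ranging from 1% to 10"%.

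For the planned combined sample the section then says "we have adequate precision to assess a doubling of detection rates", and limits this claim with "for pathogens with an incidence between 1% -7% range". The next sentence refers back to these doublings and states that "the 95% confidence intervals on the gain are expected to be approximately ± 0.6 and ± 1.8 percentage points overall", with full widths of about 1.2 to 3.6 pp, "depending on the baseline incidence".

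The planned total is also given in the Protocol Summary (Section 4): "Target sample size: 1074 (s)ARI patients (450 in hospital; 624 in PCC and ED").

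**The concern.** Read as written, the two half-widths are the ends of the range just named: ±0.6 pp at 1% and ±1.8 pp at 7%. The lower pair agrees with the stated assumptions and the upper pair does not. Because the section also mentions a wider range of 1% to 10%, a reader cannot tell whether precision is being claimed up to 7% or up to 10%, and cannot reproduce the upper figure from the inputs given. What is at stake is whether a stated precision figure is correct and traceable. The size of the study is not in question.

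**Working it through.** **Inputs, all from Section 12.9.1 (N also in Section 4)**
- N = 450 + 624 = 1,074.
- Paired design with no patient positive by A and negative by B, so the gain is the single discordant proportion.
- Doubling, so the gain equals the baseline incidence p.
- 95% confidence, two-sided, z = 1.96.

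**Formula.** With the reverse discordant cell at zero, the gain is a simple proportion, and its half-width is h = 1.96·√(p(1−p)/N).

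**The lower figure reproduces**
- p = 1%: 1.96·√(0.01·0.99/1074) = 0.595 pp, full width 1.19 pp. The protocol states ±0.6 and 1.2.

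**The upper figure does not reproduce at 7%**
- p = 7%: 1.96·√(0.07·0.93/1074) = 1.526 pp, full width 3.05 pp. The protocol states ±1.8 and 3.6.
- Difference: 1.80 − 1.53 = 0.27 pp in half-width, which is 0.27/1.53 ≈ 18%. In full width it is 3.60 − 3.05 = 0.55 pp.

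**It does reproduce at 10%**
- p = 10%: 1.96·√(0.10·0.90/1074) = 1.794 pp, full width 3.59 pp. This matches both ±1.8 and 3.6.
- Solving h = 1.8 pp for p gives 10.07%. Any half-width that rounds to 1.8 needs p between about 9.5% and 10.7%.

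**Other routes to ±1.8 at 7%, N = 1,074**

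| Variant | Half-width at 7% (pp) |
|---|---|
| Wilson | 1.53 |
| Jeffreys | 1.53 |
| Agresti–Coull | 1.54 |
| Bonett–Price (paired) | 1.54 |
| Clopper–Pearson | 1.57 |
| Without the squared term, 1.96·√(p/N) | 1.58 |
| Continuity correction 1/N | 1.62 |
| Interval on the doubled rate | 2.08 |
| Treated as unpaired | 2.58 |
| 7% read as the rate after doubling (gain 3.5%) | 1.10 |
| 90% level | 1.28 |
| 99% level | 2.01 |

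Rounding N down to 1,000 gives 1.58 pp by the basic formula. Reaching ±1.8 at 7% would need N = 1.96²·0.07·0.93/0.018² ≈ 772, which the protocol does not mention.

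**Allowing reverse discordance c.** The half-width becomes 1.96·√((p + 2c − p²)/N). Setting it to 1.8 pp at p = 7% requires p + 2c − p² = 1074·(0.018/1.96)² = 0.0906, so c = (0.0906 − 0.0651)/2 ≈ 1.27%, about 18% of the reference positives. The same share at p = 1% (c ≈ 0.18%) gives 1.96·√((0.01 + 0.0036 − 0.0001)/1074) ≈ 0.70 pp. The ±0.6 match is lost, and the section assumes c = 0 in any case.

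**The case against.** Four points can be made for the plan.

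1. **The error is conservative.** At 7% the protocol promises a wider interval than its assumptions imply, so the claim of adequate precision for 1% to 7% survives and is slightly strengthened. This stands.
2. **The figures are marked as approximate and the study is a pilot.** No hypothesis test, power claim or success criterion hangs on them. This also stands and keeps the point minor. But approximation does not cover an 18% gap at one end when the other end agrees to the first decimal.
3. **The sample size does not depend on this sentence.** A reader might infer that N is now unsupported. The protocol does not bear that out: Section 12.4 bases the recruitment targets on logistics and on patient numbers in previous years, and Section 12.9.1 reports the precision expected at a planned N rather than solving for N.
4. **The 10% origin is not proved.** This stands as well. The figures 1.8 and 3.6 both fit 10%, and 10% is the top of the scenarios described, but the protocol does not show the calculation. An interval on the doubled rate at a 5% baseline also gives 1.79 pp. That fits neither the wording, which places the interval on the gain, nor a range ending at 7%.

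A reader might also want numerical half-widths by setting and for serology. Their absence is not an error: the section already says that the setting strata will be less precise and that the serology analysis is exploratory with limited power.

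**Conclusion.** The point holds as a minor arithmetic inconsistency. Under the protocol's stated assumptions, 1% to 7% corresponds to about ±0.6 to ±1.5 pp (width 1.2 to 3.1 pp), and ±0.6 to ±1.8 pp (width 1.2 to 3.6 pp) corresponds to 1% to 10%. The two ranges as printed do not belong together.

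The conclusion rests on N = 1,074, zero reverse discordance and a gain equal to baseline incidence, all taken from Section 12.9.1. It does not depend on the interval method, since the usual intervals for the gain at 7% lie between 1.53 and 1.62 pp.

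The documents do not settle whether the 7% or the ±1.8 is the slip. The 10% scenario is the probable source of the ±1.8, and no more than that. Nor does the mismatch show that the study is too small or less precise than claimed. At 7% the direction is the opposite.

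**What to change.** Check the sponsor's calculation and align the two ranges in Section 12.9.1. Depending on what it supports, state one of the following:
- incidence 1%–7%: half-width about ±0.6 to ±1.5 pp, full width about 1.2 to 3.1 pp; or
- incidence 1%–10%: half-width about ±0.6 to ±1.8 pp, full width about 1.2 to 3.6 pp.

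The cost is one corrected sentence. Recruitment targets, data collection and analysis are unaffected.
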